9.3 Reporting Procedures

Adverse events will be reported using the designated AE form. All SAEs, medication toxicities, deaths, or hospitalizations (other than elective) occurring following administration of study product will be recorded using the SAE Form and reported to the IRB and Emergent Medical Monitor, CROMS, NIAID's designated pharmacovigilance contractor and the Independent Safety Monitor (ISM), by fax in the mandatory time frame described below, including those events deemed unrelated to the protocol. Each event will be described in detail along with start and stop dates, relationship to investigational product, action taken, and outcome. Adverse events will be assessed in terms of their seriousness, intensity, and relationship to study product. Events that resulted in planned hospital admissions or surgical procedures for an illness or disease that existed before the subject was enrolled in the study or before study product was given, are not to be considered AEs unless they cause the planned hospital admission or surgical procedure to occur at a time other than the planned date.

9.3.1 Serious Adverse Events

Any SAE, including death due to any cause, that occurs to any subject entered into treatment in this study whether or not considered related to the study product, must be reported to the Sponsor or their representative by telephone and in writing within 24 hours of the PI knowing of the event.

Following notification from the PI, Emergent will report any suspected adverse reaction that is both serious and unexpected. Emergent will notify FDA, all participating investigators (i.e., all investigators to whom the sponsor is providing drug under its INDs or under any investigator's IND) and DMID in an IND safety report of potential serious risks from clinical trials or any other source, as soon as possible, but in no case later than 15 calendar days after the Sponsor determines that the information qualifies for reporting as specified in 21 CFR Part 312.32. Emergent will also notify FDA of any unexpected fatal or life-threatening suspected adverse reaction as soon as possible, but in no case later than 7 calendar days after the Sponsor's initial receipt of the information. Relevant follow-up information to an IND safety report will be submitted as soon as the information is available. Emergent will submit to FDA any additional data or information that the agency deems necessary, as soon as possible, but in no case later than 15 calendar days after receiving the request.

All SAEs designated as "not related" to study product(s), will be reported to the FDA at least annually in a summary format.

9.3.2 Reporting of Pregnancy

A Notification of Pregnancy form will be completed for any female study subject or for any female partner of a male study subject who becomes pregnant following their exposure to

study product (Day 1) through 3 months after the last dose of study product and forwarded within 24 hours of awareness by fax or e-mail to Emergent Pharmacovigilance. All pregnancies will also be reported as a protocol deviation. The site will maintain contact through at least monthly telephone calls with pregnant study subjects to obtain pregnancy outcome information. The pregnant subject will be followed by monthly telephone calls until 2 months after the birth of the baby or until the end of the pregnancy (in case pregnancy is terminated) at which time the Pregnancy Outcome form will be completed and forwarded to Emergent Pharmacovigilance. Infants born to these study subjects will also be monitored for SAEs for up to 2 months after birth (information regarding SAEs will be captured on the Pregnancy Outcome form and the SAE form). Pregnancy Outcome forms will be limited to collecting data on the following information, should it be identified during the monthly telephone calls, at the end of the pregnancy, or at the follow-up telephone call at 2 months after birth of the baby:

- Prior maternal history including congenital abnormalities or pregnancy complications;
- Estimated date of conception;
- Estimated and actual date of delivery or pregnancy termination;
- Mode of delivery;
- Maternal complications;
- Neonatal complications (i.e. lethal or nonlethal congenital abnormality).

9.4 Type and Duration of Follow-up of Subjects after Adverse Events

The collection of laboratory data will be limited to those parameters listed in [Section 8.2.1](#). Abnormal laboratory test values or abnormal clinical findings such as heart rate will be recorded using the FDA Guidance for Industry: *Toxicity Grading Scale for Healthy Adult and Adolescent Volunteers Enrolled in Preventive Vaccine Clinical Trials September 2007* (with the exception of sodium and potassium [see [Section 9.2.1](#)]). However, the grading is modified for sodium and potassium since there is significant overlap between laboratory normal values and Grade 1 and 2 toxicity criteria using this grading scale (Section 9.2.1). The QT interval will be corrected using the Fridericia formula (QTcF). All AEs will be monitored until they are resolved or are clearly determined to be due to a subject's stable or chronic condition or intercurrent illness(es).

9.5 Dose Escalation

The SMC will review all safety and PK data after completion of each cohort. Upon completion of review by the SMC, safety summary and PK data will be sent to the FDA for review and approval to continue with dose escalation.

9.6 Study Halting Criteria

General:

- Any SAE
- Three or more subjects within a cohort, with the same Grade 2 event ;
- Any single Grade 3 or above finding (with the exception of aPTT as explained below);
- Evidence of hematemesis or hematochezia in 2 or more subjects
- Any other findings that, at the discretion of the PI, indicate that the study should be halted;

Electrocardiograph (ECG):

Two or more subjects within a cohort who meet any of the criteria below:

- PR: >220 ms
- QRS: >120 ms
- QTcF > 450 ms for men and >470 ms for women; or
- Change from baseline (average of pre-dose triplicate ECGs): QTcF >60 ms.

Decisions are to be based on an average QTcF value of triplicate ECGs. If an ECG demonstrates a prolonged QT interval, 2 more ECGs should be obtained over a 10 minute period. The averaged QTcF values of the 3 ECGs will then be used for decision making.

Laboratory criteria:

- Two or more subjects within a cohort have a Grade 3 increase in aPTT (confirmed on repeat) as defined by the FDA toxicity grading scale as modified for this study and as appropriate for the administration of UV-4B ([Appendix II](#)).

If any of the above events occur, the study will be halted and the SMC will review the available safety data to determine if the study should proceed as planned. If none of the events described above have been observed, dose escalation will proceed according to the protocol requirements.

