Description of Study Design:	
This is a multiple-ascending dose (MAD) study with up to five cohorts of healthy subjects planned. Each cohort will consist of 8 subjects (6 active; 2 placebo). Within each cohort, subjects will be randomized to receive UV-4B oral solution or placebo solution TID (every 8 hours ± 0.5) for 7 days.
 
A Safety Monitoring Committee (SMC) review of all safety and tolerability data will be conducted after completion of each cohort. The SMC will also be consulted for any specific safety signals at any point during the study, to include dose-related trends within the normal range.
 
The SMC will review all safety and PK data after completion of each cohort. Upon completion of review by the SMC, safety summary and PK data will be sent to the Food

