ALT		Trace protein, when specific gravity is higher than 1.015	Lymphocytes	
GGT			Monocytes	
LDH			Neutrophils	
Creatinine		Mucus	Differential percentages, absolute values and RBC indices	
Phosphorus		Crystals		
Bicarbonate		Ketones when blood sugar is normal		
Uric Acid				
CPK		Hyaline casts		
Chloride				
BUN		Blood (unless greater than 3 RBC/hpf and or CPK greater than 400)		
Bilirubin (total, indirect, direct)				
Lipase		Epithelial Cells		
Amylase		Bacteria < many		
		*Urine Spermatozoa		

*when urine spermatozoa are present, urine protein must be repeated if result is elevated.

10. Any known or expected risk of bleeding, such as, but not limited to:

- laboratory evidence of active bleeding, such as positive fecal occult blood, or positive urinary blood that is greater than 3 RBC/hpf (Day 1 except women who are menstruating);
- history of peptic ulcer, GI bleeding (including hematemesis, melena, bloody emesis or rectal bleeding) or bleeding from hemorrhoids;

- history of minor bleeding episodes such as, rectal bleeding (spots of blood on toilet paper), and gingival bleeding within 3 months before the first dose;
- any family history (suspected or documented) of coagulopathy;
- females with a history of dysfunctional uterine bleeding, including history of menorrhagia (heavy menstrual bleeding), metrorrhagia, or polymenorrhea;
- use of anticoagulants (i.e. warfarin or low molecular weight heparin), coagulants, anti-PLT (i.e. clopidogrel) 30 days prior to dosing;

11. Has scheduled any surgical procedure during study participation;
12. History of alcohol and/or drug abuse within 1 year prior to dosing, as judged by the PI and/or has a positive urine drug screen for substances of abuse including at a minimum marijuana, cocaine, methamphetamine, opiates, phencyclidine, barbiturates, benzodiazepines, tricyclic antidepressants, methadone, and amphetamines, at screening or check-in. Urine alcohol above 50mg/dL;
13. Has donated plasma or blood or intends to within 30 days prior to the first day of dosing and 30 days after the final day of dosing;
14. Has received treatment with any medication, either prescription or nonprescription, including dietary supplements or herbal medications (e.g., quercetin; Gingko Biloba; palmetto), within 14 days prior to dosing and is unable to refrain from any medication during the study period. Exceptions are acetaminophen (not more than 2g/day), vitamin products at recommended daily doses or hormonal birth control;

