In addition, all AEs will be graded (Grade 1 to 4) according to the FDA Guidance for Industry: *Toxicity Grading Scale for Healthy Adult and Adolescent Volunteers Enrolled in Preventive Vaccine Clinical Trials September 2007* and the *Division of Microbiology and Infectious Diseases (DMID) Adult Toxicity Table November 2007* as modified for this study ([Appendix II](#)). For clinical or laboratory observations not addressed by the toxicity grading criteria, Grade 0=absent will be used in the AE CRF to indicate the toxicity grading criteria do not apply.

Relationship to Study Products: The PI's assessment of an AE's relationship to the study product is part of the documentation process, but it is not a factor in determining what is or is not reported in the study. If there is any doubt as to whether a clinical observation is an AE, the event will be reported. All AEs must have their relationship to study product assessed using the terms: related or not related. In a clinical trial, the study product must always be suspect. To help assess, the following guidelines will be used.

Related – There is a reasonable possibility that the study product caused the AE. Reasonable possibility means that there is evidence to suggest a causal relationship between the study product and the AE. If an alternate etiology is not identified, the AE must be considered related to study product.

Not Related – There is not a reasonable possibility that the administration of the study product caused the event.

AE's should be documented from time of dose administration through the final study visit.

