9.7 Individual Dose Limiting Toxicity

- Any single grade 3 AE or Lab abnormality
- Fecal occult blood remains positive for 3 consecutive stool samples, hemorrhoids are excluded
- Evidence of frank hematemesis or hematochezia/melena of any duration
- Any clinical signs or symptoms the PI has determined is unsafe to administer IP

If an individual subject in a cohort reaches dose limit toxicity as determined by any of the above criteria, the subject will not receive any additional doses, and will be withdrawn from the study. All subjects withdrawn from the study will undergo routine follow up safety monitoring.

9.8 Safety Oversight (Safety Review Committee, Independent Safety Monitor plus Safety Monitoring Committee)

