Myalgia	No interference with activity	Some interference with activity	Significant; prevents daily activity	Emergency room visit or hospitalization

AE = adverse event; CRF = case report form
 
All graded values representing a change from baseline must be reported as AEs. For clinical or laboratory observations not addressed by the toxicity grading criteria, Grade 0 = absent will be used in the AE CRF to indicate the toxicity grading criteria do not apply.
				

Systemic (General)	Mild (Grade 1)	Moderate (Grade 2)	Severe (Grade 3)	Potentially Life Threatening (Grade 4)
Illness or clinical AE (as defined according to applicable regulations)	No interference with activity	Some interference with activity, not requiring medical intervention	Prevents daily activity and requires medical intervention	Emergency room visit or hospitalization

AE = adverse event; CRF = case report form
 
All graded values representing a change from baseline must be reported as AEs. For clinical or laboratory observations not addressed by the toxicity grading criteria, Grade 0 = absent will be used in the AE CRF to indicate the toxicity grading criteria do not apply.
				

Serum	Mild (Grade 1)	Moderate (Grade 2)	Severe (Grade 3)	Potentially Life Threatening (Grade 4)
Sodium – hyponatremia mEq/L	132 – 134	130 – 131	125 – 129	<125
Sodium – hypernatremia mEq/L	148 – 150	151 – 153	>154	Associated with seizures
Potassium – hyperkalemia mEq/L	5.3 – 5.4	5.5 – 5.6	>5.6	Associated with ECG changes
Potassium – hypokalemia mEq/L	3.0 – 3.5	2.5 – 2.9	2.0 – 2.4	≤1.9
Glucose – hypoglycemia mg/dL	65 – 69	55 – 64	45 – 54	<45
Glucose – hyperglycemia fasting mg/dL random mg/dL	100 – 110 111 – 125	111 – 125 126 – 200	>125 >200	Insulin requirements or hyperosmolar coma
Blood urea nitrogen increase mg/dL	21 – 26	27 – 31	>31	Requires dialysis
Creatinine increase mg/dL	1.5 – 1.7	1.8 – 2.0	2.1 – 2.5	>2.5 or requires dialysis
Calcium – hypocalcemia mg/dL	8.0 – 8.8	7.5 – 7.9	7.0 – 7.4	<7.0
Calcium – hypercalcemia mg/dL	10.6 – 11.0	11.1 – 11.5	11.6 – 12.0	>12.0
Magnesium – hypomagnesemia mg/dL	1.3 – 1.7	1.1 – 1.2	0.9 – 1.0	<0.9
Phosphorous – hypophosphatemia mg/dL	2.3 – 2.5	2.0 – 2.2	1.6 – 1.9	<1.6
Creatine phosphokinase – increase by factor	2.0 – 5.0 x ULN	5.1 – 10.0 x ULN	10.1 – 20 x ULN	>20 x ULN
Albumin – hypoalbuminemia g/dL	2.8 – 3.3	2.5 – 2.7	<2.5	--
Total protein – hypoproteinemia g/dL	5.5 – 5.9	5.0 – 5.4	<5.0	--

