Alkaline phosphate – increase by factor	2.0 – 2.9 x ULN	3.0 – 5.0 x ULN	>5.0 – 10.0 x ULN	>10.0 x ULN
Liver function tests – ALT, AST increase by factor	1.1 – 2.5 x ULN	2.6 – 5.0 x ULN	5.1 – 10 x ULN	>10 x ULN
Bilirubin – when accompanied by any increase in liver function test increase by factor	1.1 – 1.25 x ULN	1.26 – 1.5 x ULN	1.51 – 1.75 x ULN	>1.75 x ULN

Serum	Mild (Grade 1)	Moderate (Grade 2)	Severe (Grade 3)	Potentially Life Threatening (Grade 4)
Bilirubin – when liver function test is normal; increase by factor	1.1 – 1.5 x ULN	1.6 – 2.0 x ULN	2.1 – 3.0 x ULN	>3.0 x ULN
Cholesterol increase mg/dL	201 – 210	211 – 225	>226	--
Pancreatic enzymes – amylase, and lipase – increase by factor	1.5 – 2.0 x ULN	2.1 – 3.0 x ULN	3.1 – 5.0 x ULN	>5.0 x ULN
AE = adverse event; ALT = alanine aminotransferase; AST = aspartate aminotransferase; CRF = case report form; ECG = electrocardiogram; ULN = upper limit of normal Criteria are modified for this study based on reference values. All graded values representing a change from baseline must be reported as AEs. For clinical or laboratory observations not addressed by the toxicity grading criteria, Grade 0 = absent will be used in the AE CRF to indicate the toxicity grading criteria do not apply.				

Hematology	Mild (Grade 1)	Moderate (Grade 2)	Severe (Grade 3)	Potentially Life Threatening (Grade 4)
Hemoglobin (Female) decrease - gm/dL	10.5-11.5	9.5-10.4	8.0 – 9.4	< 8.0
Hemoglobin (Female) change from baseline value - gm/dL	Any decrease – 1.5	1.6 – 2.0	2.1 – 5.0	> 5.0
Hemoglobin (Male) decrease - gm/dL	12.5 – 13.5	10.5 – 12.4	8.5 – 10.4	< 8.5
Hemoglobin (Male) change from baseline value – gm/dL	Any decrease – 1.5	1.6 – 2.0	2.1 – 5.0	> 5.0
WBC increase - cell/mm ³	10,901 – 15,000	15,001 – 20,000	20,001 – 25,000	> 25,000
WBC decrease - cell/mm ³	2,500 – 3,500	1,500 – 2,499	1,000 – 1,499	< 1,000
Lymphocytes decrease - cell/mm ³	750 – 1,000	500 – 749	250 – 499	< 250
Neutrophils decrease – cell/mm ³	1500-2000	1000-1,499	500-999	< 500
Eosinophils increase - cell/mm ³	650 – 1500	1501 – 5000	> 5000	Hypereosinophilic
PLT decrease - /mm ³	75,000 – 99,000	50,000 – 74,999	20,000 – 49,999	<20,000
PT – increase by factor	1.0 – 1.10 x ULN	1.11 – 1.20 x ULN	1.21 – 1.25 x ULN	> 1.25 ULN
PTT – increase by factor (partial thromboplastin time)	1.0 – 1.2 x ULN	1.21 – 1.4 x ULN	1.41 – 1.5 x ULN	> 1.5 x ULN
Fibrinogen increase - mg/dL	400-500	501-600	>600	--

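### Protocol 9.6 does not name melena in its two-subject GI-bleeding halting rule, although Protocol 9.7 makes melena dose-limiting; the gap is small and one word closes it

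*Protocol*

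**What the plan says.** Two bleeding rules sit next to each other in the protocol.

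- **Study level (Protocol 9.6).** One general halting criterion is "Evidence of hematemesis or hematochezia in 2 or more subjects". It carries no within-cohort limit, unlike the Grade 2, ECG and aPTT criteria in the same section.
- **Subject level (Protocol 9.7).** One criterion for stopping and withdrawing an individual is "Evidence of frank hematemesis or hematochezia/melena of any duration".

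The other general criteria in 9.6 are any SAE, any single finding of Grade 3 or above (aPTT excepted), "Three or more subjects within a cohort, with the same Grade 2 event", and PI discretion. SAP section 6 says what a halt means: dosing stops for everyone under treatment, safety evaluation continues, and the SMC decides whether the study goes on.

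Melena also appears in Protocol 5.2, exclusion criterion 10, which excludes a history of "GI bleeding (including hematemesis, melena, bloody emesis or rectal bleeding"). Appendix II has no row for melena or GI bleeding.

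**The concern.** One episode of melena is enough to end a subject's dosing, but on the literal text it adds nothing to the study-level count of GI bleeds. Two cases of hematemesis or hematochezia stop dosing for everyone. Two cases that include melena do not, unless another criterion happens to be met.

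Bleeding is a hazard this protocol watches closely. It tests stool and all vomitus for occult blood, examines skin and mouth daily for bleeding, and excludes people at known risk of bleeding. The subjects are healthy volunteers. Up to two sites may enroll, and the PIs are blinded, so one case at each site could leave each PI looking at a single event. A written count does not depend on anyone connecting the two.

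**Working it through.** The plan gives no operating characteristics for its halting rules, so there is no stated figure to reproduce. The check is mainly a reading of the rules.

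**Step 1. Apply each 9.6 criterion to two subjects, at least one with melena.**

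| 9.6 criterion | Met? |
|---|---|
| Two subjects with hematemesis or hematochezia | No: the literal count is 0 or 1 |
| Three in a cohort with the same Grade 2 event | No: 2 < 3, and Grade 1 does not count |
| One finding of Grade 3 or above | Only if an event or a hemoglobin result reaches Grade 3 |
| Any SAE | Only if an event is judged serious |
| PI discretion | Possible, but not a count |

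The ECG and aPTT criteria concern other findings. On the Appendix II row "Hemoglobin (Female) change from baseline value - gm/dL", and on the matching row for men, Grade 3 is a fall of 2.1 to 5.0 g/dL.

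**Step 2. How melena would be graded.** Appendix II has a generic row for an illness or clinical AE. There, Grade 1 is no interference with activity and Grade 2 is "Some interference with activity, not requiring medical intervention". Grade 3 both prevents daily activity and needs intervention. Grade 4 is an emergency room visit or hospitalization. Mild melena in an ambulatory volunteer most likely falls at Grade 1 or 2. At Grade 1 no number of subjects meets a numeric rule; at Grade 2 it takes three in a cohort; at Grade 3 or 4, one is enough.

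**Step 3. Which pairs are affected.** Three bleeding types give 3 × 4 / 2 = 6 unordered pairs. The pairs without melena number 2 × 3 / 2 = 3, and 9.6 names all of these. The other 6 − 3 = 3 include melena.

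**Step 4. Exposure that remains.** A course is 3 × 7 = 21 doses. A cohort is 8 subjects, 6 on active and 2 on placebo.

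- Both cases in one cohort: 8 − 2 = 6 cohort-mates.
- First case in an earlier cohort: 8 − 1 = 7 cohort-mates.

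The timing of the second case is an assumption, as is parallel dosing of the cohort. The totals also assume that neither the PI nor the SMC acts.

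| Second case after dose | Doses left each | 6 cohort-mates | 7 cohort-mates |
|---|---|---|---|
| 3 (end of Day 1) | 21 − 3 = 18 | 108 | 126 |
| 9 (end of Day 3) | 21 − 9 = 12 | 72 | 84 |
| 15 (end of Day 5) | 21 − 15 = 6 | 36 | 42 |

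**Step 5. Illustration with assumed rates.** The documents give no melena rate. Let p be an assumed rate per active subject, with X ~ Binomial(n, p).

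| p | P(X ≥ 2), n = 6 | P(X ≥ 3), n = 6 | P(X ≥ 2), n = 18 |
|---|---|---|---|
| 0.02 | 0.006 | 0.0002 | 0.050 |
| 0.05 | 0.033 | 0.002 | 0.227 |
| 0.10 | 0.114 | 0.016 | 0.550 |
| 0.20 | 0.345 | 0.099 | 0.901 |

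The first probability column is the chance, within one cohort, that a two-subject melena rule fires. The second is the chance under the present Grade 2 rule if every case is Grade 2. The third is the two-subject rule over the active subjects of three cohorts (3 × 6 = 18), since the bullet is not cohort-limited. The comparison ignores the SAE, Grade 3 and PI-discretion routes, so it overstates the practical difference.

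**The case against.** The strongest reply is that 9.6 already means to include melena. Protocol 9.7 joins hematochezia and melena with a slash, as if they were one item, and the Amendment 1 log shows both bullets entering together. Exclusion criterion 10 does not settle the matter: it lists hematemesis beside bloody emesis, so separate listing there does not prove separate meaning. This reading is reasonable. It makes the change a clarification rather than a correction, but a halting rule should not turn on how a slash is read.

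Second, the amendment log gives reconciliation with FDA recommendations as the reason for both edits. The FDA letter is not in the documents, so the wording may have been agreed. That possibility stands; the log gives no reason for the difference.

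Third, a study rule need not mirror a subject rule. Persistent fecal occult blood is also dose-limiting in 9.7 without a count in 9.6. That is correct, and no change is proposed there. The point is narrower: this bullet already counts visible GI bleeding and leaves out one form of it. The line between visible and occult bleeding is a judgment made here, not one the protocol draws.

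Fourth, the safeguards are real. The Protocol Summary states: "The SMC will also be consulted for any specific safety signals at any point during the study". The PI can halt the study. Either the PI or the sponsor can classify a bleed as an important medical event, which makes it an SAE. Full hematology runs on Days 2 through 8. These shrink the gap but do not close it, because none is an automatic count of melena cases.

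**Conclusion.** The point holds, and it is small. On the literal text, two cases that include melena meet no numeric halting rule when they are non-serious, below Grade 3 and without a Grade 3 hemoglobin result. What remains is continued dosing of up to 6 or 7 cohort-mates for the rest of a seven-day course, unless the PI or SMC steps in.

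Three stronger readings are tempting, and the documents do not support them.

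- A reader might infer that half of two-subject bleeds would be missed. Three of six pairs is a count of labels, not a rate; nothing in the documents gives the pairs equal weight.
- A reader might infer that melena would be entered as Grade 0 and so escape grading. Protocol 9.2.1 says "Grade 0=absent will be used in the AE CRF to indicate the toxicity grading criteria do not apply", but this is for observations the criteria do not address, and the generic clinical AE row appears to address melena.
- Protocol 9.6 says escalation proceeds if none of its events occurred, so a reader might infer that a missed count lets the dose rise unchecked. Escalation follows the protocol's requirements, and Protocol 9.5 requires SMC review and FDA approval after every cohort.

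**What to change.** Add melena to the 9.6 bullet so that the events counted are hematemesis, hematochezia or melena. Keep the two-subject threshold and the absence of a within-cohort limit, and leave 9.7 as it is. If the present wording was agreed with FDA, record that and the reason instead.

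The cost is one word in a protocol amendment, with no new data collection and no effect on the analyses. The rule may fire slightly more often: at an assumed melena rate of 0.02, the chance of two or more cases among 18 active subjects is 0.050. It would fire much more often only if melena were common, which is when a pause is wanted. Each halt leads to SMC review, not termination.
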